**REGULATORY FRAMEWORK:**

Please indicate all that apply:

	DOD (Department of Defense)
	DOE (Department of Energy)
	DOJ (Department of Justice)
	ED (Department of Education)
	EPA (Environmental Protection Agency)
	FDA (Food and Drug Administration)
	HHS (Department of Health and Human Services)
	VA
	Other:

**FUNDING:**

This pilot project is not currently funded; however, we will be applying for internal funding to cover the cost of the NIRS leads and a NIRS monitor. IRB approval is required to apply for the internal funding, which is why it has not yet been received.

**CLINICAL TRIALS**

Is this a clinical trial per the NIH definition of a Clinical Trial?  Yes  No

NIH Definition of a Clinical Trial:

A research study in which one or more human subjects are prospectively assigned to one or more interventions. An "intervention" is defined as a manipulation of the subject or subject's environment for the purpose of modifying one or more health-related

PROTOCOL TITLE:

biomedical or behavioral processes and/or endpoints. Examples include: drugs/small molecules/compounds; biologics; devices; procedures (e.g., surgical techniques); delivery systems (e.g., telemedicine, face-to-face interviews); strategies to change health-related behavior (e.g., diet, cognitive therapy, exercise, development of new habits); treatment strategies; prevention strategies; and, diagnostic strategies (which may include placebo or other control) to evaluate the effects of those interventions on health-related biomedical or behavioral outcomes.

**Use the following four questions to determine the difference between a clinical study and a clinical trial:**

- 1) Does the study involve human participants?  Yes  No
- 2) Are the participants prospectively assigned to an intervention?  Yes  No
- 3) Is the study designed to evaluate the effect of the intervention on the participants?  
 Yes  No
- 4) Is the effect being evaluated a health-related biomedical or behavioral outcome?  
 Yes  No

Note that if the answers to the 4 questions are yes, your study meets the NIH definition of a clinical trial, even if...

- You are studying healthy participants
- Your study does not have a comparison group (e.g., placebo or control)
- Your study is only designed to assess the pharmacokinetics, safety, and/or maximum tolerated dose of an investigational drug
- Your study is utilizing a behavioral intervention

If yes to all 4 questions, please confirm that the research team is familiar with and agrees to comply with the investigator requirement to register the study on the ClinicalTrials.gov database. Additionally, the approved consent document(s) must be uploaded to the ClinicalTrials.gov database  Yes  No

For any assistance with registration of your trial or the requirements, please contact [contact]

PROTOCOL TITLE:

## 1. Objectives

The objective of this study is to obtain the cerebral regional oxygen saturation (cRSO2) in a preterm population that is born at altitude to determine if the range of “normal” values is different than those obtained at sea level. **We hypothesize that the cRSO2 will be lower than the normative values that have been previously described.** As more clinical studies are being performed, and the use of NIRS becomes more common, it is imperative that we assess if other factors such as altitude must be considered prior to general implementation.

**Aim 1:** We will prospectively obtain cRSO2 for the first 96 hours of life in infants born <32 weeks’ gestation. The data obtained will not be interrupted clinically as the clinicians will not be able to view the data obtained from the NIRS monitoring.

**Aim 2:** Outcome measures including death, intraventricular hemorrhage, necrotizing enterocolitis, sepsis, duration of supplemental oxygen required, time to taking full volume feeds via nipple, and hospital length of stay will be collected. This will be compared with the infant’s average cRSO2 as well as the fluctuation in cRSO2 that was observed. This may provide supportive evidence for clinical use of NIRS in future trials at UNMH.

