#### Exclusion Criteria:

- Any known cardiac anomaly or other anomaly which may impair perfusion and blood flow.
- Infant born after placental abruption or concern for extreme blood loss immediately after birth.
- Unable to consent the mother/guardian due to maternal health issues after delivering (eg requiring intubation or sedation after the delivery).
- Mothers/guardians that are prisoners, as the study team would like to have continuing communication with the mother during the study period as needed.
- Mothers/guardians that are <18 years of age will not be approached for consent.
- Any mother/guardian that is not able to consent due to having a legal representative will not be approached for consent in this study.
- Any infant that is planned to be placed for adoption
- Infant is greater than 24 hours of age at time of consent.

Individuals will be screened for eligibility by reviewing the Newborn Intensive Care Unit (NICU) census twice daily.

Any infant that has been consented for participation and completes at least 48 hours of NIRS monitoring will be included in the final study sample.

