### **11. Multi-Site Research – N/A**

### **12. Study Procedures**

Any infant that is born at <32 weeks' gestational age and does not meet exclusion criteria as described above will be considered for the study. The mother/guardian must speak English as we do not have the resources to translate the documents, nor could we obtain consent appropriately. If an infant is born at another hospital and transferred to UNMH, they will be considered for the study only if the mother/guardian is physically present.

The study will be described following the consent script (attached) and if consent is obtained, the infant will then be given a study identifier (ex. NIRS-1). The "NIRS-1" component of the identifier will be the infant's number used so that identifying information can be removed. For sub-analysis, the infants will be divided into 3 groups to assess the impact of gestational age on the measurements. Specifically, the 3 groups will be divided into the following ages: Group 1: 23 to ≤26 weeks' gestation; Group 2: >26 weeks' gestation to ≤29 weeks' gestation; Group 3: >29 weeks' gestation to 31 6/7 weeks' gestation.

The NIRS device will be applied after the infant is admitted to the Newborn Intensive Care Unit (NICU) at UNMH (ideally within the first 12 hours of life). The device will remain in place, with routine skin care management during care times, for the first 96 hours of life and then removed. This will allow 72-96 hours of data collection, depending on the timing of the placement of the NIRS device in relation to the birth time. The SpO2 (routine oxygen saturation monitoring) information will be collected at the same time so that the relative cerebral fractional tissue oxygen extraction can be calculated. The data output will not be visible to the clinical team, so there will not be any incidental clinical interpretation of this data.

To apply the device, a trimmed piece of Mepitel (MoInlycke), which is a translucent skin dressing, will be placed with the hydrocolloid adhesive-backed NIRS sensor placed

PROTOCOL TITLE:

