directly onto the Mepitel. The sensor will then be placed with the skin dressing onto the central forehead of the infant. The sensor will be plugged in to ensure that signal strength is appropriate. There will be daily inspection of the sensor site by the research team, with the area monitored by the bedside nurse with each care-time (usually every 3 hours). The area will be monitored for erythema or irritation of the skin around the sensor, and the sensor will be removed or replaced if necessary. We will avoid lifting up the sensor unless necessary for removal or repositioning. Care will be taken to avoid pressure on top of the sensor. After the infant is 96 hours of age, the sensor will be removed. Adhesive remover or a warm moist cloth will be used to slowly remove the sensor from the skin. The sensor will then be discarded after use. The NIRS probe (circled in red) is shown below in this sample image taken from van Bel, et al[6]. Additionally, the NIRS probe is plugged into a NIRS monitor, which is then plugged into the Phillips monitor if desired. We currently have 6 of the devices which connect the NIRS to the Phillips monitor, however need to purchase the NIRS monitor and the NIRS probes.

Information will be collected from the medical record at time of enrollment as well as at the time of infant discharge. This information will include: gestational age at birth, birth weight, mode of delivery, sex of infant, maternal complications during pregnancy (including pre-eclampsia, chorioamnionitis, hypertension, diabetes, thyroid disease, and cervical insufficiency), maternal medications during pregnancy, resuscitation required at birth including if chest compressions were done, length and type of respiratory support infant required, intraventricular hemorrhage, necrotizing enterocolitis, patent ductus arteriosus and if treatment was used, chronic lung disease, retinopathy of prematurity, any surgeries that were completed during the hospitalization, sepsis, hospital length of stay, time to full volume nipple of feeds, and death if applicable. The data obtained during the NIRS recording will be collected and analyzed to determine the average cerebral regional oxygen saturation. The relative cerebral fractional tissue oxygen extraction will be calculated. The blood pressure and heart rates of each infant that are normally obtained for clinical purposes will be extracted from the patient charts during the time of the NIRS monitoring.

PROTOCOL TITLE:

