### **13.Data Analysis**

The cerebral regional oxygen saturation data will be averaged for each infant. All male and female data will be analyzed separately and the compared to determine any statistical differences that are present between sexes. NIRS parameters will be summarized as median and interquartile ranges. The relative cerebral fractional tissue oxygen extraction will be calculated using the following equation:  $(SpO_2 - rScO_2)/SpO_2$ .

As described above, there will be a sub-analysis of the infants enrolled based on gestational age. Specifically, the 3 groups will be divided into the following ages: Group 1: 23 to  $\leq 26$  weeks' gestation; Group 2:  $>26$  weeks' gestation to  $\leq 29$  weeks' gestation; Group 3:  $>29$  weeks' gestation to 31 6/7 weeks' gestation. Comparisons among different groups will be analyzed by one-way ANOVA followed by Dunn's method. Categorical data will be analyzed using Fisher's test. Spearman's rank correlation coefficient will be used to calculate correlations between cerebral regional oxygen saturation, relative cerebral fractional tissue oxygen extraction and gestational age. Values of  $p < 0.05$  will be considered statistically significant.

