#### B. Neonates of Uncertain Viability or Nonviable Neonates

PROTOCOL TITLE:

*Complete this checklist if the subject population will include neonates of uncertain viability.*

Provide justification for each of the following:

1. Where scientifically appropriate, preclinical and clinical studies have been conducted and provide data for assessing potential risks to neonates.  
*Prior research has been conducted using the NIRS technology in this patient population. There have been minimal risks noted to the neonates that have the sensor in place. However, the use of this technology has not been reported at high altitude, which has the potential to directly impact the results.*
2. Each individual providing consent is fully informed regarding the reasonably foreseeable impact of the research on the neonate.  
*Each mother / guardian will provide consent and be fully informed. We expect there to be no direct benefit to the neonates in the study, however the results may inform future use in the NICU that may become routine.*
3. Individuals engaged in the research will have no part in determining the viability of a neonate.  
*The use of this technology will not impact the viability of the neonate, and the research team will not be determining the viability of the neonate in relation to this study.*
4. The research holds out the prospect of enhancing the probability of survival of the neonate to the point of viability, and any risk is the least possible for achieving that objective, or, the purpose of the research is the development of important biomedical knowledge which cannot be obtained by other means and there will be no added risk to the neonate resulting from the research  
*The results from this study have the potential to impact the routine use of this technology in the NICU and may have the ability to note if/when an infant is having an acute change in cerebral blood flow which may reflect an intraventricular hemorrhage. The purpose of this research cannot be obtained by other means and there will be no added risk to the neonate resulting from the research.*

Verify each of the following:

1. The research will not terminate the heartbeat or respiration of the neonate  
 True  
 False
2. There will be no added risk to the neonate resulting from the research  
 True

PROTOCOL TITLE:

False

---

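### Aim 2 compares haemorrhage with cRSO2 summarised over a recording in which the haemorrhage may occur, so post-bleed readings can enter the exposure

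*Combined protocol and SAP*

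**What the plan says.** **Exposure and outcomes.** Section 1, Aim 2, names seven outcomes: "Outcome measures including death, intraventricular hemorrhage, necrotizing enterocolitis, sepsis", then duration of supplemental oxygen, time to full nipple feeds and length of stay. They are to be compared with each infant's average cRSO2, "as well as the fluctuation in cRSO 2 that was observed". The same paragraph hopes that the result will support clinical use of NIRS in future trials.

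**How the exposure is formed.** Section 13: "The cerebral regional oxygen saturation data will be averaged for each infant". Section 12 likewise says that the recording is "analyzed to determine the average cerebral regional oxygen saturation". Neither section stops the average at an event, fixes an early window or states a model for Aim 2.

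**Window.** The sensor stays on until 96 hours of age. Section 12: "This will allow 72-96 hours of data collection".

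**Timing of outcomes.** Section 12 takes haemorrhage, NEC, sepsis and death from the chart. None of the fields listed there is an onset date. Section 16 refers to an attached data file that is not among the documents.

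**The signal and haemorrhage.** In Section 38.B the protocol says that NIRS may be able to note an "acute change in cerebral blood flow which may reflect an intraventricular hemorrhage".

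**The only related rule.** Section 4: a consented infant who "completes at least 48 hours of NIRS monitoring will be included in the final study sample".

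**The concern.** If a haemorrhage occurs while the sensor is on, the readings after it are part of the average and of any fluctuation measure with which haemorrhage is then compared. By the protocol's own account the bleed may alter the cerebral signal. Infants with haemorrhage could then have lower or more variable cRSO2 even if they did not differ at all before the bleed.

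An association found this way is compatible with two different accounts: low or unstable cRSO2 came before the injury, or the injury changed cRSO2. Whole-recording summaries cannot separate them. The difference matters because Aim 2 is meant to inform the clinical use of NIRS. If event dates are not captured, the order cannot be recovered from the dataset later, and Section 37 has identifiers destroyed when the study ends.

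**Working it through.** **1. The plan's window, reproduced.** Recording length = 96 h minus age at placement. Placement follows consent, and an infant is excluded if "Infant is greater than 24 hours of age at time of consent". If placement follows consent at once, 96 - 0 = 96 h and 96 - 24 = 72 h, which matches the 72-96 hours in Section 12. At the 12-hour placement goal it is 96 - 12 = 84 h.

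**2. Which outcomes can fall inside the recording.**

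| Outcome | Position |
|---|---|
| Haemorrhage | Possible at any hour of recording. The 48-hour rule does not exclude it, because an infant who bleeds early and stays monitored still qualifies. |
| NEC, sepsis | Only if onset is before 96 h. The documents give no onset times. |
| Death | No readings follow it. 48 h of monitoring is complete at 0 + 48 = 48 h to 24 + 48 = 72 h of age, which leaves 96 - 48 = 48 h to 96 - 72 = 24 h in which an included infant can die with terminal readings in a shortened average. |
| Oxygen duration, nipple feeds, length of stay | Not reached. |

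**3. Share of the data that is post-event.** With recording from 12 to 96 h and an event at age T, share = (96 - T)/(96 - 12). This applies to haemorrhage and to early NEC or sepsis, not to death.

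**4. Shift in that infant's average.** Shift = share x d, where d is a change that lasts to 96 h. The documents give no direction, size or duration for d. Falls of 5 to 15 points are assumed.

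| Event age T | Share | d = 5 | d = 10 | d = 15 |
|---|---|---|---|---|
| 24 h | 72/84 = 86% | 4.3 | 8.6 | 12.9 |
| 48 h | 48/84 = 57% | 2.9 | 5.7 | 8.6 |
| 72 h | 24/84 = 29% | 1.4 | 2.9 | 4.3 |

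A change that recovers before 96 h would shift the average less.

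**5. Fluctuation.** The plan does not define the measure. If it were the within-infant SD, a step of d points alone contributes d x sqrt(p(1 - p)), where p is the post-event share. The square root is 0.35, 0.49 or 0.45 for p = 86%, 57% or 29%. For d = 5 to 15 this gives 1.7-5.2, 2.5-7.4 or 2.3-6.8 points.

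**6. Group comparison.** The figures in step 4 are per affected infant. Bleeds after 96 h add no shift and dilute the group difference. If half of bleeds fall inside the recording and are spread evenly over it (mean share one half), a 10-point fall gives 0.5 x 0.5 x 10 = 2.5 points; if 90% do, 0.9 x 0.5 x 10 = 4.5 points. A bleed before placement works the other way, because every reading is then post-bleed.

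**7. Illustration of the test.** The simulation used 100 infants, 84 h of recording, no cRSO2 difference before the bleed, a Mann-Whitney test at two-sided 0.05 and 3,000 trials per scenario. Assumed ranges were haemorrhage in 10-30% of infants, 50-90% of bleeds inside the recording and falls of 5-15 points. The between-infant SD was held at 7 and not varied. The whole-recording average gave a significant difference in 8% to 96% of trials, and pre-bleed data alone in 4.4% to 5.8%. For 20% haemorrhage, half inside the recording and a 10-point fall, the figures were 25% and 5%. The pre-bleed result assumes that onset is known exactly, which the chart will not provide.

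**The case against.** **Aim 2 makes no predictive claim.** It says that outcomes will be compared with cRSO2. Section 38.B describes detection, for which a signal change at the bleed is relevant. This stands. A reader might infer that the protocol asserts that cRSO2 precedes injury, but the text does not say so. It is why the full-recording comparison can stay as a description, provided it is labelled as having no direction.

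**Death is different.** A reader might infer that the average can be a consequence of death. It cannot, because death ends the recording and infants who die before completing 48 hours of monitoring are outside the final sample. What remains is that terminal readings enter a shortened average.

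**Most of Aim 2 is untouched.** Three of the seven outcomes are not reached, and two depend on onset times that the documents do not give. The firm case is haemorrhage. Replacing the exposure throughout Aim 2 is not justified.

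**The size is assumed.** This is correct. Only the time shares follow from the protocol's schedule. A range of 8% to 96% in the simulation shows that the error rate is undetermined, and no single figure should be cited as this study's bias.

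**The attached file may hold event dates.** It may, so the documents do not support saying that dates will not be collected. Dates without an analysis rule would still leave Section 13 as it is.

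**Haemorrhage is dated only between scans.** This stands and limits the remedy. Counting bleeds first documented after an early window would still admit bleeds that began inside it, so the ordered analysis has to rest on a negative scan.

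**Conclusion.** The point holds for haemorrhage. Followed as written, Aim 2 lets post-bleed readings into both named exposures, and no rule in the plan separates them. It extends to NEC and sepsis only where onset is before 96 hours, and to death only through terminal readings in infants who die after completing 48 hours of monitoring. Aim 1 is not in question.

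For recording from 12 to 96 hours, 86%, 57% or 29% of the data are post-event for a bleed at 24, 48 or 72 hours. Any shift in points rests on an assumed sustained change. The group difference also depends on how many bleeds fall inside the window, which the documents do not say. The mechanism is established from the text; its size is not. This is an inexpensive improvement to a pilot study and does not invalidate it.

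**What to change.** 1. Keep the full-recording average for Aim 1, for the outcomes not reached, and as a descriptive Aim 2 comparison labelled as association without direction.
2. Extract from the chart, unless already in the attached data file, the dates of the last negative and first positive routine head scan, of NEC and sepsis onset, and of death. Storing them as age in hours fits the de-identification in Section 16. No new scans are needed.
3. For haemorrhage, add an analysis that uses only cRSO2 recorded before the last negative scan, with the same cut-off age applied to comparison infants. The alternative is a fixed early window restricted to infants with a negative scan at or after its end. Report separately, as undated, infants whose first scan is already positive.
4. For NEC and sepsis, use cRSO2 before the documented onset in the same way. For death, use a fixed early window among infants alive at its end.
5. Treat the fluctuation measure in the same way as the average.
6. Base any statement that cRSO2 precedes injury only on items 3 and 4.

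**Cost:** a few extra chart dates, and fewer events and less recording per infant in the ordered analyses. Haemorrhage onset will still be known only to an interval, so the ordered analysis reduces the problem and loses the undated infants.

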## 2. Background

Near-infrared spectroscopy (NIRS), is a technology that can provide continuous, non-invasive monitoring of oxygenation in tissue[1]. Light absorption is measured at a few discrete wavelengths which can provide information for the tissue oxygen saturation in multiple organs[2], with cerebral, renal and splanchnic oxygenation being the most commonly measured in neonates[1]. NIRS technology was first available in 1977, however different sensors and manufacturers resulted in a large range of regional oxygen saturation (RSO2), making it difficult to establish normative values within a specific population[1]. Thus, improvements in the technology has resulted in the ability to consider more clinical uses for the NIRS technology.

Infants with congenital heart disease is a population in which the NIRS technology has been applied. The use of cerebral oximetry measurement has provided the first indication of a clinical problem in 23% of the procedures in which the technology was utilized[1]. While some initial studies have shown a negative correlation between cerebral regional oxygen saturation (cRSO2) and gestational age[3], routine use in the preterm infant has not been established.

Infants born prematurely (<37 weeks’ gestation), and especially those born extremely preterm (<28 weeks’ gestation), have organs that are immature and vulnerable. There are fluctuations in cerebral blood flow due to limitations in autoregulation, which may be exacerbated by routine care of the infant[4]. Previously there was a limitation in the ability to monitor these changes in blood flow and saturations, however NIRS now provides the technology needed. There are clinical trials ongoing to assess cRSO2 immediately after birth in an attempt to improve outcomes[5] as well as monitoring in the first 72 hours of life in extremely preterm infants[4]. While these studies will likely provide support for applying NIRS as routine care for preterm infants, there is data lacking when infants are born at altitude. It is unknown if the increased altitude in places such as Albuquerque and Denver would result in a different range of expected values with NIRS monitoring. Thus, we proposed a prospective observational study in which we apply NIRS monitoring to

PROTOCOL TITLE:

infants born <32 weeks' gestation for the first 96 hours of life to assess the cRSO2 as well as outcome information for the infant.

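### Every Section 13 test that could serve Aim 2 is unadjusted for gestational age, which the protocol itself links to both cRSO2 and outcome risk

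*Combined protocol and SAP*

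**What the plan says.** **Aim 2 (Section 1).** The outcomes are death, IVH, "necrotizing enterocolitis, sepsis, duration of supplemental oxygen required, time to taking full volume feeds via nipple, and hospital length of stay will be collected". They are to be compared with the infant's average cRSO2 "as well as the fluctuation in" cRSO2. That is seven outcomes (four binary, three durations) by two exposures, or 14 comparisons.

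**Section 13** does not mention Aim 2 or its outcomes. It offers:

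- a per-infant mean: the "cerebral regional oxygen saturation data will be averaged for each infant";
- a comparison by sex, and medians with interquartile ranges;
- one-way ANOVA with Dunn's method, placed directly after the three GA groups;
- Fisher's test, in a general sentence that begins "Categorical data will be analyzed using";
- correlations by Spearman's method, limited to three variables: "rank correlation coefficient will be used to calculate correlations between cerebral regional oxygen saturation, relative cerebral fractional tissue oxygen extraction and gestational age";
- a 0.05 threshold for significance.

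**GA elsewhere.** Section 12 explains the GA groups: "the infants will be divided into 3 groups to assess the impact of gestational age on the measurements". GA is on the data collection list: "This information will include: gestational age at birth, birth weight, mode of delivery, sex of infant". Section 2 reports that initial studies "have shown a negative correlation between cerebral regional oxygen saturation" and GA. Section 18 places a high risk of sepsis, necrotizing enterocolitis (NEC), severe brain injury and death particularly in the lowest GA group.

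**The concern.** GA is a foreseeable confounder on the protocol's own account: it is linked to the exposure in Section 2 and to outcome risk in Section 18. The tests that could be stretched to cover Aim 2 all leave it out.

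The direction of the error depends on the sign of the GA-cRSO2 correlation:

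- **Negative, as cited.** Less mature infants have higher cRSO2 and worse outcomes. A real link between low cRSO2 and worse outcome is then hidden, and a spurious result associates high cRSO2 with worse outcome.
- **Positive.** A link between low cRSO2 and worse outcome is exaggerated.

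The cited correlation appears to come from the cohort that Section 5 describes as 30 to 42 weeks (both sections give the same reference). Its sign and size below 32 weeks are therefore uncertain. Section 1 hopes that Aim 2 will support clinical use of NIRS in later trials at the site, so an error in either direction would carry forward.

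**Working it through.** **Plan's own figure.** The only one is the target of 100 infants. It rests on a precedent, with no effect size, SD or power, so nothing can be reproduced. What follows is illustration: n = 100 is from Section 5, and every correlation, odds ratio and incidence is an assumption.

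**Step 1. Which Section 13 tests can reach Aim 2?** Spearman lists only cRSO2, oxygen extraction and GA. Fisher's test could cover the four binary outcomes if cRSO2 were categorised, but no cut is given. ANOVA could compare cRSO2 between outcome groups if read generously. None of these adjusts for GA.

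**Step 2. Durations, no true link, no deaths.** Let a be the GA-cRSO2 correlation and b the GA-duration correlation. The induced correlation is r = a × b, and z = atanh(r) × sqrt(97). Rejection is P(Z > 1.96 - z) in the positive direction and P(Z < -1.96 - z) in the negative. With a = -0.3:

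| b | r | z | positive | negative | simulated Spearman, total |
|---|---|---|---|---|---|
| -0.2 | 0.06 | 0.59 | 8.6% | 0.5% | 9% |
| -0.3 | 0.09 | 0.89 | 14.2% | 0.2% | 14% |
| -0.5 | 0.15 | 1.49 | 31.9% | <0.1% | 31% |
| -0.8 | 0.24 | 2.41 | 67.4% | <0.1% | 67% |

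Nearly all rejections are positive: high cRSO2 with longer duration. GA-partial Spearman stays at about 5%. With a = 0 the unadjusted test also holds 5%. With a = -0.1 it rejects 5/6/8/12% across the four rows.

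**Step 3. Durations, true partial correlation -0.3, no deaths.** The marginal correlation is r = ab - 0.3 × sqrt((1 - a²)(1 - b²)). With a = -0.3:

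| b | r | power, correct direction (Fisher z) | simulated Spearman |
|---|---|---|---|
| -0.2 | 0.060 - 0.280 = -0.220 | 60% | 55% |
| -0.3 | 0.090 - 0.273 = -0.183 | 45% | 41% |
| -0.5 | 0.150 - 0.248 = -0.098 | 16% | 14% |
| -0.8 | 0.240 - 0.172 = +0.068 | <1% | <1% |

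In the last row the marginal sign reverses. Adjusted for GA, atanh(0.3) × sqrt(96) = 3.03 gives 86% by Fisher z; simulated GA-partial Spearman gives about 80%. Ranks cost a few points throughout. If a is +0.3 instead, the mean unadjusted correlation is -0.32 to -0.40, against -0.17 to -0.28 at a = 0.

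**Step 4. Binary outcomes.** Unadjusted ANOVA of cRSO2 by outcome group, 17% incidence, GA odds ratio 0.65 per week. As a goes from 0 to -0.3, null rejection rises from about 5% to 18%. Power at a true odds ratio of 2 per SD lower cRSO2 falls from about 58% to 21%. GA-adjusted penalised logistic regression keeps 56-58%. At a = 0 the two methods have the same power, so the loss comes from GA.

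**Step 5. Deaths.** An infant who dies has a shortened stay and may never reach full nipple feeds. Assume b = -0.7 and a GA odds ratio for death of 0.65 per week, and enter deaths as short durations.

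- True partial correlation -0.3, mortality unrelated to cRSO2: power of GA-partial Spearman falls from about 81% to about 48% at 8% mortality and 29-34% at 17%.
- No duration link, but low cRSO2 doubling the odds of death per SD: GA-partial Spearman rejects in the wrong direction in about 20-22% of studies at 8% mortality and 41-43% at 17%.
- Survivors only: error about 5% and power about 72-77%.

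GA adjustment of the durations is therefore not enough without a rule for deaths.

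**The case against.** The sizes rest on inputs that the documents do not give. The protocol states no GA correlation for the durations or for fluctuation, and the cited GA-cRSO2 correlation comes from older infants. The 67% figure needs both extremes at once, and many cells lie between 5% and 9%. Aim 2 is worded tentatively, sits in a pilot and is not the stated hypothesis. GA is collected, so adjustment could be added later. All of this stands, and it limits the weight of the point. It does not supply an adjusted analysis, and choosing one after the data are seen leaves the analyst free to pick.

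Three stronger readings are tempting and are not supported:

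- *The missing fluctuation measure and the missing duration test are errors in their own right.* On their own they are unfinished detail. The substantive fault is the unadjusted comparison.
- *Binary outcomes would lose most of their power because Fisher's test needs cRSO2 cut in two.* The protocol states no cut. ANOVA of cRSO2 by outcome group is an equally possible reading and loses nothing at GA-cRSO2 zero.
- *Unadjusted results will falsely favour low-saturation monitoring.* Under the sign the protocol cites, spurious results point the other way.

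**Conclusion.** The point holds and should be fixed. Aim 2 as planned has no analysis that separates cRSO2 from GA, although the protocol links GA to both sides of the comparison. At GA-cRSO2 -0.3, with 100 infants and no deaths, the illustrated null rejection is about 9/14/31/67% for durations. Power in the correct direction is about 55/41/14/<1%, against about 80% adjusted. The size shrinks quickly with weaker correlations and the inflation vanishes at GA-cRSO2 zero. The sign below 32 weeks is not known, which is itself a reason to adjust. A reader might infer that the study's main result is compromised. It is not: Aim 1, the cRSO2 range at altitude, does not depend on this analysis.

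**What to change.** Add to Section 13:

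> Aim 2 is exploratory and exempt from the p<0.05 rule. Fluctuation is the within-infant SD of cRSO2. The association of each of the seven outcomes with average cRSO2 and with this SD (14 estimates, all reported) will be adjusted for GA as a continuous covariate. For the three durations, GA-partial Spearman correlation will be used among infants who survive to discharge, with the number of deaths reported beside each and death analysed as its own outcome. For death, IVH, NEC and sepsis, Firth-penalised logistic regression will be used, with the cRSO2 measure kept continuous and GA as the single covariate. Estimates are given with 95% confidence intervals; unadjusted results are secondary.

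**Cost.** One paragraph and no new data. For binary outcomes the standard error of the cRSO2 effect rises by about 0-13% with no true link (for example 0.37 to 0.40 at 8% incidence) and by up to about 18% with the assumed link. Intervals will be wide where events are few. The duration results apply to survivors only and lose some power (about 72-77% against about 80% in the illustration, at 8-17% mortality). Confounding by illness severity remains.
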